After HBV infects the human body, its partially double-stranded relaxed circular DNA (rcDNA) together with HBV DNA polymerase enters into the nucleus. With the assistance of host DNA repair mechanisms, rcDNA is converted into covalently closed circular DNA (cccDNA), which serves as the template for viral replication. cccDNA binds to host histones and non-histone proteins to form a highly stable viral minichromosome [5,6]. Due to the long half-life of cccDNA, progeny rcDNA generated through transcription and reverse transcription can replenish the nuclear cccDNA pool without requiring new viral entry, it maintains a persistent transcriptional template. When cccDNA continues to exist, some progeny rcDNA replenishes the nuclear cccDNA pool, and others acquire an envelope through the endoplasmic reticulum–Golgi complex to form viral particles that are secreted from hepatocytes into the bloodstream [5,7].

Because of this unique and complex replication mechanism, HBV cannot be completely eradicated. The persistence of cccDNA in hepatocyte nuclei means that even patients who achieve apparent recovery, as indicated by serological markers, remain at lifelong risk of viral reactivation [5,8].

Currently, the main antiviral drugs used in CHB include interferons (IFNs) and nucleos(t)ide analogues (NAs) [2,9–11]. NAs mainly inhibit viral replication by blocking the reverse transcription process. They are administered orally, easy to use, and generally well tolerated [5,18,19]. However, because NAs do not directly inhibit cccDNA transcriptional activity, they fail to effectively suppress the production of viral proteins such as HBsAg expression. As a result, HBsAg declines slowly during treatment, and the annual clearance rate of HBsAg remains only 0–

1.3% under the long-term NAs therapy, and this means CHB patients require indefinite treatment [5,12,13]. IFNs exert a dual effect by enhancing host immune responses and directly inhibiting viral replication at multiple stages [14–16]. In addition to suppressing viral replication, IFNs also inhibit cccDNA transcription, promote cccDNA degradation, and facilitate the clearance of HBV-infected cells, thus favoring viral elimination. In some patients, HBsAg declines rapidly during IFN therapy. Previous studies, varying by selected populations, reported HBsAg seroclearance rates of 2.8–7% after 48 weeks of IFN monotherapy, which are higher than those observed with NAs monotherapy. And its benefits may continue even after IFN discontinuation [17–19]. However, IFNs require subcutaneous injection and are associated with adverse effects such as bone marrow suppression and flu-like symptoms, leading to relatively poor tolerability.

Pegylated interferon (PegIFN) in combination with NAs has become a recent focus of clinical practice and research. As these drugs target different aspects of the viral life cycle, their combination may produce additive or synergistic effects, potentially improving efficacy [19,20]. Combination therapy with PegIFN and NAs can be applied either as initial therapy or sequential therapy. In the former, PegIFN and NAs are administered together as first-line treatment in treatment-naïve CHB patients. In the latter, PegIFN is added to or substituted for NAs in patients who have already achieved a virological response with NAs. Whether PegIFN plus NAs provides clear additional benefit compared with PegIFN or NAs alone, or whether it merely increases patient burden with limited additional benefit, remains controversial. Details regarding treatment indications, timing of initiation, and duration of combination therapy remain debated. Regarding this issue, existing studies are often limited by sample size, geographical region, or study population, provide inconsistent results. Most studies include fewer than 1,000 patients, with follow-up typically limited to 1–2 years. Due to limited sample size and duration, evaluation of long-term outcomes such as HCC incidence or decompensated cirrhosis is difficult. Consequently, most studies use HBsAg loss as the primary endpoint.

For example, retrospective analyses of previous studies show that although PegIFN plus NAs as initial combination therapy yields significantly higher HBsAg clearance rates than NA monotherapy, comparisons with PegIFN monotherapy yield inconsistent results. Sequential PegIFN therapy after NAs also improves HBsAg clearance compared with continued NA monotherapy, but few studies compare it directly with PegIFN monotherapy [12,13,17,20–27]. Improvements in fibrosis observed with PegIFN sequential therapy suggest additional benefit over NAs alone, but comparative data remain limited. Patients treated with PegIFN show a lower

incidence of HCC compared with NA monotherapy, but comparative data among PegIFN monotherapy, sequential therapy, and initial combination therapy are lacking. Regarding treatment duration, whether extending PegIFN therapy beyond the currently recommended 48 weeks provides additional benefit remains uncertain. Some studies report that extending therapy to 72 or 96 weeks in HBeAg-negative patients yields higher HBsAg clearance rates than 48 weeks, though without statistical significance due to small sample sizes [28,29]. Other studies indicate that extending sequential PegIFN therapy to 96 weeks after NA-induced HBeAg clearance does not significantly improve HBsAg clearance compared with 48 weeks [24].

Therefore, the advantages and disadvantages of different antiviral strategies for CHB—particularly their effects on long-term outcomes such as HCC and decompensated cirrhosis—remains insufficient. Large-scale, long-term, high-quality clinical studies are urgently needed to provide robust evidence for optimizing antiviral regimens.

This study aims to establish a nationwide, multicenter, real-world cohort to compare long-term outcomes under different treatment regimens. The goal is to generate high-quality evidence to guide treatment and follow-up of chronic viral hepatitis, support optimization of therapeutic strategies, and accelerate progress toward a functional cure.

2 Aims

To explore the long-term outcomes of antiviral therapy for CHB with the incidence of HCC as the primary endpoint, in order to identify optimal clinical decision-making strategies for the management of CHB.

3 Study design

This is an observational, multicenter, real-world study led by Huashan Hospital. Approximately 98 sub-centers are expected to participate. Randomization and blinding are not involved in this study. It will only observe and collect data related to the changes of clinical indicators during routine treatment. The physicians will make clinical decisions based on the applicable guidelines and evidence at the time of enrollment, combined with clinical experience and patient-specific conditions. No additional interventions will be imposed, and clinical decisions will not be influenced by this study.

The study consists of three cohorts (Figure 1):

Prospective cohort (PS cohort): Patients enrolled before the implementation of Protocol Version 3.0 who were planned or currently undergoing antiviral therapy. Clinical data will be prospectively collected for five years after informed consent has been obtained. The total follow-up period will last five years.

Retrospective-prospective cohort (RPS cohort): Patients received antiviral therapy whose initial clinical visit occurred before Protocol Version 3.0 but signed informed consent after its implementation. The study will retrospectively collect treatment and examination records from baseline (defined as the date patient first visited the study center for CHB starting from September 2020, with concurrent HBV DNA, liver function, and abdominal ultrasound results) and will prospectively collect subsequent clinical data up to five years from baseline. The total follow-up period will last five years.

Retrospective cohort (RS cohort): Patients receiving antiviral therapy whose clinical records from September 2020 until the implementation of Protocol Version 3.0 will be retrospectively collected.

[figure not shown]

Figure 1 Schematic diagram of the study design

Patients enrolled at sites before Version 3.0 are assigned to the PS cohort, those enrolled before Version 3.0 belong to the RS cohort, and whether to belong to the RPS cohort is depending on

patients' willingness. Patients at newly added sites after Version 3.0 are included in the RS cohort, and may, depending on patients' willingness, be included in the RPS cohort.

4 Eligibility Criteria, Exclusion Criteria, and Withdrawal Criteria

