4.1 Inclusion Criteria

- 1) Chronic HBV infection (HBsAg positive for ≥6 months, or <6 months with liver histology consistent with CHB and other liver diseases excluded);
- 2) Age ≥18 years;
- 3) Planned or currently receiving potent low-resistance NAs [entecavir (ETV), tenofovir disoproxil fumarate (TDF), tenofovir alafenamide fumarate (TAF), or tenofovir amibufenamide (TMF)], or planned to receive PegIFNα-2b, either treated or treatment-naïve;
- 4) Written informed consent.

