6.1 Clinical Information to be Collected

6.1.1 The collection information and time point of PS Cohort

Starting from September 2020, outpatient or inpatient patients with CHB who meet inclusion criteria and have been screened through the exclusion criteria will be enrolled after informed consent. Baseline data and scheduled follow-up assessments will be collected at fixed time points after treatment initiation. Recommendations are based on the guidelines and clinical evidence. Actual schedules may be adjusted by treating physicians. No additional visits will be imposed by the study [2].

A recommended follow-up schedule and assessments are summarized in Table 1.

Table 1 Study visit table

	Baseline	V1	V2	V3	V4	V5	V6	V7	V8	V9	V10	V11	V12	V13
Study week	0	4±1	12±2	24±4	36±4	48±4	72±4	96±4	120±4	144±4	168±8	192±8	216±8	240±8
Time point	0	1m	3m	6m	9m	1y	1.5y	2y	2.5y	3y	3.5y	4y	4.5y	5y
Demographics	★													
Height & weight	★													
Medical history	★													
Family history	★													
Clinical assessment														
Symptoms and signs	★			★	★	★	★	★	★	★		★		★
Treatment regimen	★			★	★	★	★	★	★	★		★		★
Clinical events ^a	★	★	★	★	★	★	★	★	★	★	★	★	★	★
Laboratory tests														
Quantitative HBsAg	★	★	★	★	★	★	★	★	★	★	★	★	★	★
HBeAg, anti-HBe, anti-HBc, anti-HBs	★	★	★	★	★	★	★	★	★	★	★	★	★	★
HBV DNA	★	★	★	★	★	★	★	★	★	★	★	★	★	★
Complete blood count	★	★	★	★	★	★	★	★	★	★	★	★	★	★
Hepatic panel	★	★	★	★	★	★	★	★	★	★	★	★	★	★
Creatinine	★			★		★		★		★		★		★

AFP & CEA	★			★		★		★		★		★		★
INR & PT	★			★		★		★		★		★		★
TC, TG, HDL-c, LDL-c	★			★		★		★		★		★		★
Glucose	★			★		★		★		★		★		★
HbA1c														
Creatine kinase														
Electrolytes (K, P, Ca)														
Urinalysis														
Imaging^b and liver pathology														
Transient elastography	★			★		★		★		★		★		★
Abdominal ultrasound	★			★		★		★		★		★		★
Abdominal MRI														
Abdominal CT														
Liver biopsy														

a Clinical events include decompensated cirrhosis, HCC, death, or liver transplantation

b If abdominal ultrasound is unavailable, MRI or CT may be used as an alternative and will be treated as required completion items

c The study does not mandate MRI/CT/liver histology, but when these tests are performed in routine care, their results will be collected to enrich observational data

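### Written consent is required of every patient, which contradicts a records-only RS cohort, and RPS counts time that patients must survive in order to sign

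*Protocol*

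**What the plan says.** **Consent.** Section 4.1 lists "Written informed consent" as item 4 of the inclusion criteria, with no exception by cohort. Section 13 says that all eligible patients sign. Section 14 recruits from outpatient clinics and wards and has study staff see the patient to obtain the signature. None of the three mentions a waiver or a different route for RS.

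**Cohorts (Section 3).**
- PS: enrolled before Version 3.0, with data collected prospectively after consent. Section 6.1.1 agrees that patients "will be enrolled after informed consent".
- RPS: patients "whose initial clinical visit occurred before Protocol Version 3.0 but signed informed consent after its implementation". Baseline is the first visit to the center for CHB from September 2020 "with concurrent HBV DNA, liver function, and abdominal ultrasound results", and the five years of follow-up run from that baseline.
- RS: "Patients receiving antiviral therapy whose clinical records from September 2020 until the implementation of Protocol Version 3.0 will be retrospectively collected". Section 6.1.3 repeats this. No consent step is named, and neither PS nor RPS patients are excluded.

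**Assignment (text under Figure 1).** The rule printed is "Patients enrolled at sites before Version 3.0 are assigned to the PS cohort, those enrolled before Version 3.0 belong to the RS cohort". The same sentence then leaves RPS membership to what the patient is willing to do. For new sites: "Patients at newly added sites after Version 3.0 are included in the RS cohort", with RPS again left to willingness.

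**Primary objective (Section 8.1.1).** Comparison of the 5-year incidence of HCC between treatment regimens.

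**The concern.** Cohort membership and the consent basis belong in a protocol, and here they disagree. Section 3 reads as though a patient's agreement plays no part in RS. Sections 4.1(4), 13 and 14 say that nobody enters without it. Sites that follow different sections will fill RS differently, above all with regard to patients who have died.

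This matters for an HCC endpoint because HCC is often fatal. If entry requires a signature some years after the clock started, patients who developed HCC and died in between are absent, while those who stayed well are present with all of their event-free time. Incidence over the pre-signature period then comes out too low, provided that patients with HCC die faster than those without. In RS this depends on how the contradiction is settled. In RPS it follows from the cohort definition.

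**Working it through.** The protocol states no figure for this point, so there is nothing to reproduce. The check is a comparison of the text, one date calculation and one illustration.

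**1. RS under each reading.**

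| | RS without consent | Consent applied to RS as written |
|---|---|---|
| Section 3 (RS definition, new sites) | fits | fits poorly: inclusion is unconditional and only RPS depends on willingness |
| Sections 4.1(4), 13, 14 | wrong for RS | fit |
| Who is in RS only | patients who did not sign | patients who sign after Version 3.0 but decline follow-up or lack the RPS baseline tests |
| Patients who died without consenting | can be kept | cannot enter |

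In the right-hand column the signature comes after Version 3.0, because a patient who consented and enrolled earlier is PS. All RS data end at Version 3.0, so the whole of an RS-only patient's observed time precedes the signature.

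**2. RPS.** The definition requires a first visit before Version 3.0 and a signature after it. Section 6.1.2.2 gives an example with baseline in October 2020 and consent in December 2023. That is 38 months, and 38/60 = 63% of the five-year follow-up (36/60 = 60% with the protocol's rounding to 3 years). This patient could not have entered without surviving those months. Only 60 − 38 = 22 months are observed after consent.

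**3. PS.** As Section 3 defines it, collection starts after consent, so this selection does not arise.

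**4. Illustration for RPS pre-consent time.** Every rate here is an assumption; none comes from the protocol. Let h be the HCC rate per year, d mortality without HCC, m the excess mortality after HCC, and T the years from baseline to consent.

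- Seen among those alive at T: A / (A + exp(−hT)), where A is the integral from 0 to T of h·exp(−hs)·exp(−m(T−s)) ds. The term d cancels because it applies to everyone.
- True cumulative incidence with competing death: h/(h+d) · (1 − exp(−(h+d)T)).

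Example with h = 0.01, d = 0.01, m = 0.3, T = 3:
- A = 0.01944 and exp(−0.03) = 0.97045, so seen = 0.01944/0.98989 = 1.96%.
- True = 0.5 · (1 − exp(−0.06)) = 2.91%.
- Ratio = 0.675.

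Grid of h 0.005, 0.01, 0.02; d 0, 0.005, 0.01, 0.02; m 0.1, 0.3, 0.5; T 1 and 3:

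| Case | Seen / true |
|---|---|
| Lowest (h 0.005, d 0, m 0.5, T 3) | 0.521 |
| Highest (h 0.02, d 0.02, m 0.1, T 1) | 0.962 |
| m = 0, all other values | 1.00 to 1.03 |

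The understatement is produced by m. Without excess mortality after HCC there is none. The model uses one date T both for the end of HCC ascertainment and for survival. It therefore fits RPS time up to consent, but not RS, where ascertainment stops at Version 3.0 and the signature comes later.

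**5. The sentence under Figure 1.** As printed, enrolment before Version 3.0 leads to both PS and RS. The definitions above the figure differ in the direction of data collection, so the intent can be guessed, and a word may have been lost in translation. The text does not say whether an RPS patient also counts in RS.

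**The case against.** The best counter-argument is that Section 3 favors the reading without consent. A patient who signs after Version 3.0 is RPS, subject to the baseline tests, so RS-only patients are most naturally those who did not sign. The deceased then stay in RS, and the only fault is that Sections 4.1(4), 13 and 14 were not updated. This stands as far as it goes: the loss of deceased patients from RS is conditional and not established. A waiver may also exist in ethics papers that are not part of the protocol. It does not remove the contradiction, because Section 13, where a waiver would be expected, says the reverse.

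A second argument is that survival to consent is inherent in any design that looks back and then forward, and that delayed entry is a matter for the SAP. That is fair on method. It does not help RS if consent is kept there, since no RS-only time falls after the signature, and it cannot decide whether deceased patients may be included.

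Third, the PS clock is not entirely settled: Section 6.1.1 times assessments from treatment initiation, and 4.1(3) admits patients already on treatment. Section 3 points to consent as the start, and the statement about PS above relies on that.

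A reader might infer three stronger claims that the document does not support:
- **That the study's 5-year HCC incidence is up to 48% too low** (1 − 0.521 = 0.479). That figure rests on assumed rates and covers pre-consent RPS time only. Cohort sizes and the pooled effect are unknown.
- **That the comparison of regimens is biased in a known direction.** That would need mortality and consent patterns by regimen, which the protocol does not give.
- **That patients are definitely double-counted between PS and RS.** The sentence is more likely a wording slip, and analysis sets are left to the SAP.

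**Conclusion.** The contradiction is real and should be resolved. Universal written consent and a records-only RS cohort with unconditional entry cannot both stand as written. If consent is enforced for RS, patients who died before they could sign are excluded and HCC incidence in RS is probably understated, assuming excess mortality after HCC. If it is not enforced, three sections of the protocol are wrong for that cohort.

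The RPS limitation holds on either reading: its pre-consent time, about 38 of 60 months in the protocol's example, is conditional on survival to consent. Neither the size of the bias nor its effect on the comparison between regimens can be derived from the document. The sentence under Figure 1 is a minor wording matter. Confidence is medium, because an ethics waiver for RS may exist elsewhere.

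**What to change.** 1. Reconcile Sections 4.1(4), 13 and 14 with RS. Limit written consent to PS and RPS, and state the ethics-approved basis for using RS records, including those of deceased patients where the ethics committees allow it.
2. If consent is kept for RS, say that RS is conditional on survival to signature, and do not report its incidence as unselected.
3. Do not report incidence from RPS pre-consent time as unselected. One way is a sensitivity analysis with delayed entry, in which RPS patients count as at risk only from consent, and only if free of HCC at that date.
4. Correct the sentence under Figure 1 so that it separates PS from RS, state whether RS and RPS are nested, and count each patient once.

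**Cost.** Protocol wording; an ethics clarification at the participating sites (about 98 sub-centers, each with its own ethics approval); some record extraction for deceased patients; and fewer RPS person-years in the sensitivity analysis (22 instead of 60 months for the patient in the protocol's example). No visits or data items are added.

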4.1 Inclusion Criteria

- 1) Chronic HBV infection (HBsAg positive for ≥6 months, or <6 months with liver histology consistent with CHB and other liver diseases excluded);
- 2) Age ≥18 years;
- 3) Planned or currently receiving potent low-resistance NAs [entecavir (ETV), tenofovir disoproxil fumarate (TDF), tenofovir alafenamide fumarate (TAF), or tenofovir amibufenamide (TMF)], or planned to receive PegIFNα-2b, either treated or treatment-naïve;
- 4) Written informed consent.

4.2 Exclusion Criteria

- 1) Hepatocellular carcinoma (diagnosed or planned for treatment) or liver failure at baseline;
- 2) Concurrently participating in other interventional clinical trials;
- 3) Any other conditions deemed unsuitable by investigators or preventing compliance with study requirements.

4.3 Withdrawal Criteria

- 1) Request to withdraw at any time;
- 2) Investigators determine continuation is not in the patient's best interest;
- 3) Occurrence of clinical Objectives, including HCC, liver transplantation, or death;
- 4) Lost to follow-up.

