4.4 Lost to Follow-up Criteria

Patients in the PS or RPS cohort who fail to return within 13 months and cannot be contacted after at least two phone calls (each at least 24 hours apart) or other attempts via registered mail, courier, or email will be classified as lost to follow-up.

Exception: If patients notify investigators in advance of inability to attend a scheduled visit or examinations due to special reasons, this is not considered lost to follow-up. In such cases,

investigators should encourage patients to undergo examinations at other medical institutions and provide results through appropriate forms.

5 Sample Size Estimation

As an observational real-world study, sufficient sample size is needed to reflect real-world conditions and balance patient heterogeneity. Based on the number of participating centers and patient flow, approximately 33,000 patients are expected to be enrolled for analysis.

6 Study Procedures

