8.1 Effectiveness

8.1.1 Primary Objectives:

To compare the 5-year incidence of HCC under different treatment regimens.

8.1.2 Secondary Objectives:

- 1) Compare the 1-year, 2-year, 3-year, 4-year, and 5-year rate of HBsAg seroclearance and HBsAg seroconversion under different treatment regimens.
- 2) Compare the 5-year incidence of decompensated cirrhosis and its complications under different treatment regimens
- 3) Compare the 5-year incidence of cirrhosis under different treatment regimens
- 4) Compare proportion of patients with improvement or progression of liver fibrosis under different treatment regimens
- 5) Compare the 5-year incidence of liver transplantation under different treatment regimens
- 6) Compare the 1-year, 2-year, 3-year, 4-year, and 5-year HBsAg levels, the decline changes of HBsAg from baseline, the rate of HBeAg seroconversion, the decline changes of HBV DNA from baseline, and the proportion of HBV DNA undetectable (<20 IU/mL) under different treatment regimens
- 7) Compare the relapse rate after treatment cessation under different treatment regimens

8.1.3 Exploratory Objectives:

Describe the demographic characteristics of patients in the real-world clinical setting.

8.1.4 Methods for Assessing Efficacy Endpoints:

8.1.4.1 HCC: According to the 2019 National Health Commission diagnostic criteria for hepatocellular carcinoma, a diagnosis of HCC will be considered confirmed when either pathological or clinical criteria are met. Pathological confirmation requires diagnosis by two or more pathologists as hepatocellular carcinoma. Clinical diagnosis requires at least one typical imaging features about nodules and liver cancer on dynamic contrast-enhanced MRI, dynamic contrast-enhanced CT, contrast-enhanced ultrasound, or hepatocyte-specific contrast (Gd-EOB-DTPA) MRI; a diagnosis is established if either of the following is satisfied: 1) any nodule size ≥ 2 cm with one typical imaging feature; 2) all nodules sizes ≤ 2 cm with two typical imaging features. During follow-up, any HCC event must include recording of pathology reports (including

subtype, differentiation, and presence/distribution of intravascular tumor clusters) or imaging descriptions (including imaging modality that showed typical HCC features and nodule size), and scanned copies of original reports must be provided for centralized verification by the study team.

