8.1.4.2 Decompensated cirrhosis: According to 2019 Chinese Society of Hepatology guidelines on the management of liver cirrhosis, a diagnosis of cirrhosis will be considered confirmed when either pathological or clinical criteria are met, and when clinical manifestations suggest decompensated will be considered to be decompensated cirrhosis [31]. Pathological confirmation requires diagnosis by two or more pathologists as decompensated cirrhosis. Clinical criteria require that endoscopic evidence of esophagogastric varices, ultrasound or CT findings suggesting cirrhosis or portal hypertension, or liver stiffness measurement [LSM] values reaching corresponding thresholds. Clinical features of decompensation include ascites, variceal hemorrhage, spontaneous bacterial peritonitis/sepsis, hepatic encephalopathy, or hepatorenal syndrome, confirmed by laboratory tests, imaging, or clinical scoring systems. On occurrence of decompensated cirrhosis during follow-up, investigators must document pathology (including number of pseudo-lobules, inflammation and fibrosis staging), or supporting ancillary test results (e.g., presence of varices, imaging features suggesting cirrhosis/portal hypertension, specific LSM values, ascites, variceal bleeding), and laboratory or clinical records indicating decompensation (e.g., temperature, cognitive assessment scales, inflammatory markers, blood ammonia, liver and renal function). Original reports and scans must be provided for verification by the study team.

8.1.4.3 Changes in HBsAg, HBeAg, and HBV DNA will be analyzed by comparing baseline and follow-up values.

8.2 Safety Objectives:

Observe the drug safety under different regimens

9 Adverse Event Recording

Adverse event (AE) is any unfavorable medical occurrence in a research participant, not necessarily having a causal relationship with the study. Serious adverse event (SAE) or reaction is any untoward medical occurrence that results in death, life-threatening, requiring or prolonging hospitalization, persistent or significant disability or incapacity, congenital anomaly or birth defect, or an important medical event in the investigator's judgment.

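### Section 4.3(3) makes HCC a withdrawal reason and nothing provides for recording events afterwards, so decompensation and transplantation after HCC would be lost to two 5-year secondary objectives

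*Protocol*

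**What the plan says.** Protocol section 4.3 gives four withdrawal reasons: patient request, the investigator's judgement, loss to follow-up and, as item 3, "Occurrence of clinical Objectives, including HCC, liver transplantation, or death". It does not say what withdrawal stops, and no other section provides for recording events after it.

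Section 8.1.2 includes two affected secondary objectives. Item 2 is "Compare the 5-year incidence of decompensated cirrhosis and its complications under different treatment regimens" and item 5 is "Compare the 5-year incidence of liver transplantation under different treatment regimens". Neither is limited to events before HCC.

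Section 8.1.4.2 ties the documentation duty for decompensation to follow-up: "On occurrence of decompensated cirrhosis during follow-up, investigators must document pathology".

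Section 3 plans five years of data. For the PS cohort, "Clinical data will be prospectively collected for five years after informed consent has been obtained"; for the RPS cohort, the study "will prospectively collect subsequent clinical data up to five years from baseline". Table 1 has a clinical-events row marked at every visit to year 5, with the footnote "Clinical events include decompensated cirrhosis, HCC, death, or liver transplantation". None of these places mentions what happens after HCC.

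**The concern.** HCC stands in the same list as patient request and loss to follow-up, which are exits from the study. A site reading 4.3 would ordinarily close the patient's record once HCC is confirmed. A later decompensation or transplantation then falls outside follow-up and is not entered, although the objectives call for its 5-year incidence.

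Two things are at stake. First, the incidences in objectives 2 and 5 would be understated as worded. Secondly, a regimen with more HCC would lose more of these events, so a regimen difference that acts through HCC would be attenuated. What is collected is fixed in the protocol: an SAP can choose how to treat HCC in the analysis, but it cannot restore missing records.

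**Working it through.** **Text check.** There is no figure in the protocol to reproduce on this point. The sample size of about 33,000 in section 5 rests on centres and patient flow, and no event rates are given. Reading the sections together:

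- 4.3(3) ends participation at HCC, and no section continues event recording afterwards.
- 8.1.4.2 requires documentation of decompensation only while the patient is in follow-up.
- 8.1.2, items 2 and 5, ask for 5-year incidence without an HCC limit.
- The HCC event itself is recorded before withdrawal takes effect, so the primary endpoint is intact.

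**Illustration of size.** All rates below are assumptions.

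Inputs: 5-year HCC risk pH = 1–4%; 5-year risk without HCC pE = 0.05–0.2% for transplantation and 1–4% for decompensation; death after HCC 0.15 per year; HR = hazard of the event after HCC relative to before. Hazards are constant over 5 years, and events are counted over all enrolled patients.

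Formulas:

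- h = −ln(1 − pH)/5 and e = −ln(1 − pE)/5
- Captured = e/(h + e) × (1 − exp(−5(h + e)))
- Missed = ∫ from 0 to 5 of h·exp(−(h + e)u) × [HR·e/(HR·e + 0.15)] × (1 − exp(−(HR·e + 0.15)(5 − u))) du
- Missed share = missed/(captured + missed)

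Worked case, transplantation, pH = 2% and pE = 0.1%: h = 0.00404, e = 0.00020, captured = 0.0990% (9.90 per 10,000). Missed per 10,000 is 0.08 at HR 1, 0.40 at HR 5 and 1.58 at HR 20. The shares are 0.08/9.98 = 0.8%, 0.40/10.30 = 3.8% (from unrounded values) and 1.58/11.48 = 13.7%.

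Worked case, decompensation, pH = 2% and pE = 2%: captured = 1.980% (198.0 per 10,000). Missed per 10,000 is 1.6, 7.7 and 28.4 at HR 1, 5 and 20, giving shares of 0.8%, 3.8% and 12.5%.

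Range over all assumed inputs:

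| HR after HCC | Transplantations missed | per 10,000 patients | Decompensations missed | per 10,000 patients |
|---|---|---|---|---|
| 1 | 0.4–1.6% | 0.02–0.3 | 0.4–1.6% | 0.4–6.3 |
| 5 | 1.9–7.5% | 0.1–1.6 | 1.9–7.4% | 2–30 |
| 20 | 7–24% | 0.4–6.3 | 6–23% | 7.5–102 |

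**Effect on a regimen comparison.** Take HCC 2% against 1%, with equal risk before HCC. The captured risk ratio is 0.995 at every HR.

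- Transplantation (0.1%), full collection: 0.999, 1.015 and 1.069 at HR 1, 5 and 20. Captured over full is 0.995/1.015 = 0.98 at HR 5 and 0.995/1.069 = 0.93 at HR 20.
- Decompensation (2%), full collection: 0.999, 1.014 and 1.06. Captured over full is 0.98 at HR 5 and 0.94 at HR 20.

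**Dependence on the estimator.** The shares above count events over everyone enrolled. If the analysis instead censors at HCC, the constant-hazard model returns 1 − exp(−5e) = pE. At HR 1 that is no shortfall, and the captured ratio of 0.995 becomes a cause-specific hazard ratio of 1.0. Understatement then arises only if the hazard rises after HCC.

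**The case against.** The strongest reply is that this is ordinary drafting. Every withdrawal reason shortens planned follow-up, section 3 makes no exception for patient request or loss to follow-up either, and Table 1 is only a recommended schedule. That stands: a reader might infer that the five-year plan and 4.3(3) contradict each other, but a planned duration with a list of early exits is not a contradiction. What remains is the gap between the exit rule and objectives 2 and 5.

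A second reply is that incidence before HCC is a legitimate target whose definition belongs in the SAP, which was not available here. That is right for the analysis, but not for the records. If nothing is collected after HCC, the SAP is left with the pre-HCC version whether or not it was wanted.

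A third is that the effect is small and rests on assumed rates. This also stands. The primary endpoint is untouched, and the HCC difference itself is still measured there.

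A reader might also infer that cohorts differ in capture, because 4.3 names no cohort while 4.4 speaks of "Patients in the PS or RPS cohort who fail to return within 13 months". The protocol does not support that. Section 4.4 is a return-visit rule, which cannot apply to chart extraction. Sections 6.1.2.1 and 6.1.3 collect records already generated, with no stated stop at HCC. The point is therefore confined to prospective follow-up.

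**Conclusion.** The point holds as a gap in data collection, not as a contradiction. HCC is a stated exit, nothing continues event recording after it, and on the ordinary reading later decompensation and transplantation are lost in the PS cohort and the prospective part of the RPS cohort. The protocol does not forbid continued recording, so the loss depends on sites following that reading.

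The size cannot be derived from the document. Under the assumed rates, and counting over all enrolled patients, about 2–7.5% of these events are missed at a fivefold hazard after HCC and about 6–24% at a twentyfold hazard. With HCC 2% against 1%, the risk ratio is lowered by about 2% at fivefold and by about 6–7% at twentyfold. If the analysis censors at HCC, there is no shortfall unless the hazard rises after HCC. A reader might infer a serious bias in the regimen comparisons or harm to the primary result; neither is supported. This is an inexpensive improvement worth making while follow-up can still capture the events.

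**What to change.** In 4.3(3), state that HCC ends time at risk for the HCC endpoint only. State also that the Table 1 clinical events (decompensated cirrhosis, liver transplantation and death, with dates) continue to be recorded from routine records until death, loss to follow-up, withdrawal of consent or five years. If stopping at HCC is intended, say so and restate objectives 2 and 5 as incidence before HCC.

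The first option costs some extra data entry and no added visit or procedure. If 1–4% of 33,000 patients develop HCC, that is 330 to 1,320 patients. With about 2.0 years alive on average between HCC and year 5 (at the assumed 15% yearly death) and half-yearly visits, there are about 4 entries each: 330 × 4 = 1,320 to 1,320 × 4 = 5,280 in total. This is an upper bound, because the RS cohort has no prospective follow-up. The second option costs only the rewording of two objectives.
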